#### VII.4. Additional 60-day outcomes.

- a. Time to death: Days from randomization to death, censored at day 60, will be compared using a Cox proportional hazards regression model, adjusted for sex, fracture type, and country. Kaplan-Meier curves displaying times to death by study arm will be presented. For those with missing data on vital status at day 60, we will search the National Death Index. If death month and year are available but the day is missing, day 15 will be used as an estimate of the date.
- b. Worsened walking ability: Subjects are coded as “worsened” if at day 60 they needed a level of assistance in walking greater than prior to surgery, or if they could not walk at all, or if they died prior to day 60. Specifically, those who could walk without human assistance at baseline are considered to have worsened if at day 60 they required assistance to walk (e.g. cane, walker or human assistance), could not walk at all, or died prior to day 60; Those who required a cane or walkers at baseline are considered worsened if they needed human assistance to walk or could not walk at day 60, or if they died prior to day 60.
- c. Death or transition to institutional residence at 60 days: We will ask patients their residence locations before hospital admissions. We will also assess a location of residence on or around post-randomization day 60 via blinded telephone interview with the patient or their proxy. The analysis for this endpoint will include all individuals who were admitted from home or retirement home. Individuals who died before 60 days or reported change of residence location (including nursing home, acute rehabilitation, acute care hospital, and other) at the 60 day interview will have “positive” responses; individuals remained at home or independent living retirement home will have “negative” responses. Subjects without a valid admission location, or a 60-day vital status and valid residence location, will be excluded from the analysis. This outcome will be analyzed as a binary variable.
- d. Disability score (optional): The disability score will be calculated based on the answers to Questions 1-12 in the World Health Organization Disability Assessment Schedule 2 (WHODAS 2.0) Short Version. When only one item is missing a value, the mean score of the other items will be the assigned score to the missing item. When more than one item is missing, a summary score will not be calculated. Of note, for subjects who were not able to provide their own responses to the WHODAS assessment, data was collected from an alternate (proxy) respondent as described in the main study protocol. Proxy scores will be used if there is no patient score. If scores from both patient and proxy are available, the one with fewer missing/NA items will be used. This variable will be analyzed using a linear regression model, adjusted for sex, fracture type, country, age, and baseline disability score. This score will be analyzed with linear regression models, stratified by sex, fracture type, country, and baseline value if relevant. The normality assumption will be assessed and if it is violated, normalization transformation will be applied before the analysis.

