## **II. Quality Control Prior to Unblinding**

Prior to unblinding, we will review the distributions of each variable to be included in the analysis, aggregated across treatment arms, to identify any outlying values that may be inaccurate and should be checked. To the extent possible, inaccuracies will be resolved and the database updated with the correct values. Data that are clearly incorrect but cannot be corrected will be excluded from the analyses. Data that are unusual but not impossible, and cannot either be verified or corrected, will remain in the analysis.

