The walking ability component of the primary outcome will be assessed by a telephone interview with the subject conducted as close to day 60 as possible; information obtained during a 31-90-day window after randomization will be considered acceptable for analysis. To assess walking ability, respondents were asked to indicate whether on average in the 7 days prior to the interview they used/received human assistance to ambulate. Individuals indicating that they did not ambulate at all over the 7 days preceding the interview were coded as having met the study outcome. Vital status will be assessed at the day 60 telephone interview; for patients who cannot be reached for the 60-day telephone interview, vital status at 60 days will be assessed via telephone follow up at subsequent time points. Additional information on deaths prior to day 60 will be obtained from site Adverse Event reports and via a National Death Index search for patients who were randomized at US sites and for whom sufficient identifying information is available. Patients who are known to have died by day 60 will be assessed as having met the primary outcome, regardless of walking status assessments prior to that point. Those known to be alive at day 60 but without a response to the question about capability of walking 10 feet will be considered to be missing the primary outcome. In cases where patients were unable to provide their own responses to the primary outcome assessment (e.g., due to dementia or acute illness), data were collected from alternate (proxy) respondents as described in the main study protocol. Subjects for whom information on both components of the primary endpoint are missing (i.e., patient has become lost to follow-up so that neither survival status nor walking ability is known) will be excluded from the primary analysis, but a variety of sensitivity analyses, described below, will be conducted to assess the potential influence of these exclusions on the comparison of outcomes.

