## VI. Secondary Outcome Analyses

VI.1. 60 day mortality. This component of the primary endpoint will be assessed via site reports of deaths and at the day 60 telephone interview, and will be analyzed as a binary outcome using the MH method, stratified by sex, fracture type, and country. Patients who are unable to be assessed directly or by proxy at the 60-day telephone interview but who are known to be alive at later time points will be categorized as alive at day 60. Additional information on deaths prior to day 60 will be obtained via a National Death Index search for patients who were randomized at US sites with sufficient identifying information and for whom no follow-up at or beyond day 60 is available. The Breslow-Day test will be used to assess homogeneity of the RRs across strata.

VI.2. Ability to walk 10 feet without human assistance at 60 days post-randomization. This component of the primary endpoint will be analyzed as a binary outcome, using the MH test stratified by sex, fracture type, and country. Participants who died prior to completing the 60 day interview or had no informative answer to the ambulation assessment will be excluded from the analysis.

VI.3. New-onset delirium. This outcome will be determined by baseline and post-operative 3D CAM tests. Subjects will have a baseline 3D-CAM assessment prior to randomization and assessments on days 1, 2 and 3 post-surgery, with fewer assessments if discharged, withdrawn, or died prior to day 3. Only subjects with a baseline 3D-CAM assessment but no delirium will be included in the analysis. Subjects with a positive response on any post-surgery assessment will be classified as positive for new onset delirium. Subjects who had 1 or more post-surgery assessments with none positive for delirium will be classified as negative for this outcome. Subjects without any post-surgery 3D-CAM response will be excluded from this analysis. This binary outcome will be analyzed using the MH method, stratified by sex, fracture type, and country. The Breslow-Day test will be used to assess homogeneity of the RRs across strata.

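### Setting a missing day of death to the 15th, with no bound at dates already known, can give impossible or misclassified times in the exploratory 60-day time-to-death analysis

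*SAP*

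**What the plan says.** SAP section VII.4.a defines the outcome and model: "Time to death: Days from randomization to death, censored at day 60, will be compared using a Cox proportional hazards regression model". It then names the source for patients whose status is unknown: "For those with missing data on vital status at day 60, we will search the National Death Index". The imputation rule follows directly: "If death month and year are available but the day is missing, day 15 will be used as an estimate of the date".

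The section does not require the imputed date to fall on or after randomisation, discharge or last contact. It also gives no rule for a death month that contains day 60.

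Three other places bear on the point:

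- Section VI.1 (60-day mortality) uses the National Death Index for US-site patients with adequate identifiers and "for whom no follow-up at or beyond day 60 is available". It gives no rule for a missing day.
- Section V (primary outcome) draws on the same index and states: "Patients who are known to have died by day 60 will be assessed as having met the primary outcome". It too has no missing-day rule.
- Section II (quality control) has the only general rule on faulty values: "Data that are clearly incorrect but cannot be corrected will be excluded from the analyses". It does not mention imputed dates.

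**The concern.** A mid-month default does little harm when follow-up runs for years. Here the whole time axis is 60 days, and the imputed date can be wrong by about two weeks. The rule also ignores information that the trial holds. The randomisation date is always known, and section VI.4 needs the discharge date, so many patients have a later date on which they were known to be alive.

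Two different faults can follow. The first is an impossible time: death before randomisation, or before the last date known alive. A time below zero cannot be used in the Cox model or the Kaplan-Meier curves. The second is a time that looks valid but carries the wrong event status at day 60. At stake are the validity of individual records in one exploratory analysis, and the need for an ad hoc decision about them if no rule is set beforehand.

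**Working it through.** **Inputs.** The rule, the time origin and the day-60 censoring come from SAP section VII.4.a. The SAP gives no count of deaths lacking a day, so there is no planned figure to reproduce. All percentages below are shares of deaths with a missing day. They assume randomisation dates spread evenly over a 365-day year and deaths spread evenly over the days stated.

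**Formula.** Imputed time = (15th of death month) − (randomisation date).

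**Examples.**

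| Randomised | Day 60 | True death | True day | Imputed day | Result |
|---|---|---|---|---|---|
| 20 March | 19 May | 28 March | 8 | −5 | impossible |
| 31 March | 30 May | 31 March | 0 | −16 | impossible (worst case) |
| 10 March | 9 May | 5 May | 56 | 66 | event becomes censored |
| 20 March | 19 May | 28 May | 69 | 56 | censored time becomes an event |

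A fifth case: a patient randomised on 5 March, discharged alive on 20 March (day 15) and dying later in March is dated 15 March (day 10). That is five days before the patient is known to have been alive.

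**When a time is negative.** Randomisation must fall on the 16th or later and death in the same calendar month. The longest possible gap is 31 − 16 = 15 days, so for deaths after day 15 the share is zero.

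**Share of negative times.** Count the pairs of randomisation day and death day that meet this condition.

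- Deaths on days 0-60 (61 days): a 31-day month gives 16 × 17 / 2 = 136 pairs, a 30-day month 15 × 16 / 2 = 120, and February 13 × 14 / 2 = 91. Over the year, 7 × 136 + 4 × 120 + 91 = 1,523. Then 1,523 / 365 = 4.17 death days per randomisation date, and 4.17 / 61 = 6.8%.
- Deaths on days 5-60 (56 days): the monthly counts fall to 66, 55 and 36. Over the year, 7 × 66 + 4 × 55 + 36 = 718. Then 718 / 365 = 1.97, and 1.97 / 56 = 3.5%.

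**Share moved past day 60.** If day 60 falls on day d of a month, with d from 1 to 14, deaths on days 1 to d of that month are truly within 60 days but are dated to the 15th, after day 60. Per month this is 1 + 2 + … + 14 = 105, and per year 12 × 105 = 1,260. Then 1,260 / 365 = 3.45. This is 3.45 / 61 = 5.7% of deaths on days 0-60, or 3.45 / 56 = 6.2% of deaths on days 5-60.

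**Share moved inside day 60.** If day 60 falls on the 15th or later, deaths in the rest of that month are pulled in. The yearly count is again 1,523, or 4.17 days per randomisation date. This is about 14% of deaths on days 61-90 (4.17 / 30) or 7% of deaths on days 61-120 (4.17 / 60). The percentage depends on the window chosen.

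A day-by-day count over every randomisation date in three assumed calendar years (2017-2019) agrees with these shares. It puts the mean absolute error of the imputed date at about 7.6 days.

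**The case against.** The strongest reply is that the reach is narrow, and most of that reply stands.

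- **Early deaths.** The rule sits beside an index search for patients without day-60 vital status, while negative times need a death in the first 15 days. Section VII.1 has site staff record in-hospital death from the medical record, and sections V and VI.1 use site reports. Such deaths will mostly have exact dates. A reader might assume front-loaded deaths and reach larger shares (13.8% with a half-life of 20 days, 20.9% with 10 days). Those scenarios put the weight on the deaths least likely to lack a day, so they should not be used. The wording does not limit the rule to index records, however, and an early death after discharge with no known day remains possible.
- **Other outcomes.** A reader might infer that the imputed date decides day-60 status for the primary outcome and for 60-day mortality. The SAP does not say so. The rule appears only in VII.4.a, and section V counts patients known to have died by day 60. A death dated only to a month containing day 60 is arguably not known to meet that condition.
- **Lost deaths.** A reader might infer that negative times would be dropped and real deaths lost. The SAP says nothing about how software would treat them, and the section II review of distributions would probably reveal a negative value. But section II then offers only correction or exclusion. A wrong-side date, or one before last contact, would not stand out in a distribution.
- **Direction.** Errors at day 60 run both ways, and the rule is the same in both arms. No bias between arms has been shown.
- **Convention.** Mid-month imputation is simple and prespecified. That is a merit, but it does not justify a date that the trial's own data rule out.

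**Conclusion.** The point holds for the exploratory time-to-death analysis. As written, the rule can produce impossible times, and separately it can misclassify event status at day 60. Nothing elsewhere in the SAP repairs either fault.

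The expected effect is small. Among deaths with a missing day, the share of negative times is probably at or below the low end of the 3.5% to 7% range, because that range treats early deaths as no more likely than later ones to have a date. The share moved past day 60 is about 6%. Both figures rest on even spreads of randomisation dates and deaths, which are assumptions. With ten such deaths, the expected numbers would be about 0.35 to 0.7 negative times and 0.6 events moved out. The actual number of records is not given. The documents do not support a claim about the primary outcome, 60-day mortality or a difference between arms.

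**What to change.** Replace the imputation sentence in SAP section VII.4.a with a bounded rule. When only month and year are known, set the death to the midpoint of the feasible interval. That interval runs from the latest of the first of the month, the randomisation date and the last date known alive, to the end of the month. Negative times, and deaths before last contact, then cannot occur. For a patient randomised on 20 March who died that month with no later contact, the interval is 20-31 March and the midpoint is (20 + 31) / 2 = 25.5, so day 5 or 6 depending on the stated rounding.

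Bounding does not settle the side of day 60. For randomisation on 10 March and death in May with no contact in May, the interval is 1-31 May, and day 60 (9 May) lies inside it. For any record whose interval straddles day 60, report the time-to-death result twice: once with the death counted as an event by day 60, and once with the patient censored at day 60. A short clause could also say whether the rule is confined to VII.4.a.

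The cost is one SAP sentence and a line of code, plus a second run of the model if any record straddles day 60. It uses dates that the trial already collects.

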## **V. Primary Outcome Analysis**

The primary endpoint of the study is whether or not the subject is alive and capable of walking 10 feet or across a room without human assistance at 60 days post-randomization. As per the study protocol, the day 60 assessment will be performed within a window of 31-90 days post-randomization, although every effort will be made to make the assessment as close to day 60 as

possible. Results of assessments performed outside the 31-90 day window will be considered as missing data. The treatment effect will be evaluated using the Mantel-Haenszel (MH) test for difference in proportions, stratified by sex, fracture type, and country. The MH relative risk (RR) of spinal anesthesia (SA) vs. general anesthesia (GA) will be reported. *The Breslow-Day test* (Breslow and Day, 1980) will be used to test homogeneity of the RRs across strata. If there is statistically significant heterogeneity, we will report separate RRs within strata.

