**VII.2. Time to first in-hospital ambulation after randomization (days).**

Time from randomization to first ambulation, censored at hospital discharge, will be compared using a Cox proportional hazards regression model, adjusted for sex, fracture type, country, and use of cane or walker at baseline. Kaplan-Meier curves displaying times to first ambulation by study arm will be presented.

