#### **VIII. Subgroup Analyses**

We will evaluate treatment difference in the subgroups defined by the following stratification variables:

- a. Sex: Male vs. Female, defined as per stratification
- b. Fracture type: Femoral neck vs intertrochanteric/subtrochanteric, defined as per stratification
- c. Country of enrollment: Canada vs US
- d. Need for assistive devices to ambulate prior to fracture: present vs. absent
- e. Age category: “oldest old” (85 years and over) vs all others
- f. History of Alzheimer’s disease or other dementia: present vs absent
- g. History of chronic obstructive pulmonary disease or asthma: present vs absent
- h. History of coronary artery disease or prior myocardial infarction: present vs absent
- i. Community residence prior to fracture: home or independent living retirement home vs nursing home, rehabilitation or acute care hospital vs other.

The first step will be to test for interaction between treatment and variable defining the subgroups. Analysis within subgroups will be performed for any variable showing an interaction yielding a p-value of 0.20 or less. Subgroup analyses will be analyzed similarly as for primary analysis.

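### The two coding rules for worsened walking ability overlap, so a patient with the same cane or walker before surgery and at day 60 is worsened under one rule and not under the other

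*SAP*

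**What the plan says.** SAP section VII.4.b defines the outcome in three steps.

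- **Lead sentence.** A subject has worsened if "at day 60 they needed a level of assistance in walking greater than prior to surgery", or could not walk, or died before day 60.
- **Rule 1.** It states that "those who could walk without human assistance at baseline are considered to have worsened if at day 60 they required assistance to walk". The examples of assistance given are "e.g. cane, walker or human assistance". Inability to walk and death also count.
- **Rule 2.** It states that "Those who required a cane or walkers at baseline are considered worsened if they needed human assistance to walk or could not walk", these being the patient's day-60 states. Death before day 60 also counts.

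Three other places bear on how to read these rules. In section V the primary endpoint is being "alive and capable of walking 10 feet or across a room without human assistance at 60 days post-randomization", where the phrase concerns human help only and does not exclude device users. Section VII.2 adjusts for "use of cane or walker at baseline". Section VIII plans a subgroup by "Need for assistive devices to ambulate prior to fracture: present vs. absent".

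**The concern.** The baseline groups of the two rules are not mutually exclusive. Walking without human assistance is compatible with using a cane or walker, so rule 1 takes in every device user who needed no human help, and rule 2 takes in the same people. For one of their possible day-60 states the rules give opposite codes, and the SAP does not say which prevails.

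That state is the no-change state: same device before and after. Under rule 1 a baseline device user escapes being coded as worsened only by discarding the device, that is, by improving. Counting stable patients as deteriorated defeats the purpose of the outcome and raises its event rate, most of all among device users, whom section VIII treats as a subgroup. Two analysts working in good faith could get different relative risks from the same data. If the question is settled after unblinding, it becomes a choice made with knowledge of the results.

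**Working it through.** The SAP states no figure for this outcome, so the check is one of logic. I crossed baseline status with day-60 status for patients who walked without human help at baseline and applied the lead sentence and both rules to each pair. Cane and walker are treated as one level of assistance, as rule 2 treats them.

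| Baseline | Day 60 | Lead sentence | Rule 1 | Rule 2 |
|---|---|---|---|---|
| No aid | No aid | Not worsened | Not worsened | Does not apply |
| No aid | Cane or walker | Worsened | Worsened | Does not apply |
| No aid | Human help, cannot walk, or died | Worsened | Worsened | Does not apply |
| Cane or walker, no human help | No aid | Not worsened | Not worsened | Not worsened |
| Cane or walker, no human help | Cane or walker | **Not worsened** | **Worsened** | **Not worsened** |
| Cane or walker, no human help | Human help, cannot walk, or died | Worsened | Worsened | Worsened |

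Exactly one pair conflicts: a device at baseline and a device at day 60.

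**Size.** Let d be the share of all patients who used a device without human help at baseline, and u the share of those who still walk with a device and no human help at day 60. Rule 1 adds d × u to the event proportion obtained under rule 2. The SAP gives neither d nor u. With assumed ranges of 30–50% for d and 50–70% for u:

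- low end: 0.30 × 0.50 = 0.15
- high end: 0.50 × 0.70 = 0.35

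So 15% to 35% of all patients would change code. This is illustrative only.

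**Effect on the relative risk.** Write p_S and p_G for the event proportions under rule 2 in the spinal and general anesthesia arms. If d × u is the same in both arms, the relative risk under rule 1 is

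RR₁ = (p_S + du) / (p_G + du),

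so that

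RR₁ − 1 = (p_S − p_G) / (p_G + du).

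Under rule 2 the corresponding quantity is (p_S − p_G) / p_G. The distance from 1 therefore shrinks by the factor p_G / (p_G + du), which is below 1 whenever du is above 0. This depends on the added events being balanced between arms. If they are not, the relative risk still changes, but the formula no longer gives by how much.

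**The case against.** The best reply is that section VII.4.b shows its own intent. The lead sentence sets the governing definition, and the two rules elaborate it. Under that definition an unchanged cane user has not worsened. Moreover, rule 2's triggers are a strict subset of rule 1's. If rule 1 really covered device users, rule 2 could never alter anyone's code and would have no function. The only reading that gives each sentence a purpose is that rule 1 means patients with no aid and rule 2 means device users. The outcome is also exploratory, and section VII estimates a Mantel-Haenszel relative risk for binary outcomes only if there are enough events.

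Much of this stands. The intent can be recovered, a careful analyst would probably code it that way, and the primary endpoint and the secondary walking outcome (VI.2) do not use this definition. The numerical range rests wholly on assumed shares, and attenuation of the relative risk requires balance between arms.

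The contradiction remains all the same. Rule 1 as written gives the wrong code for a stable device user. An analyst who carries the phrase over from section V, where it concerns human help only, will apply rule 1 to device users. The SAP does not say that rule 2 overrides rule 1.

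**Conclusion.** The concern holds. The definition contradicts itself for one combination, a cane or walker at baseline and again at day 60. Rule 1 codes it as worsened, while rule 2 and the lead sentence code it as not worsened.

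The SAP itself treats baseline device users as a group to be adjusted for and analyzed separately, so the combination should not be assumed to be rare. Its frequency cannot be derived from the document. The 15–35% of all patients applies only if rule 1 is coded literally and the assumed shares are about right, and the finding does not depend on it. The reach is limited to one exploratory outcome. The correction should still be made, because an outcome definition should yield one code per patient.

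**What to change.** Make the baseline groups mutually exclusive in section VII.4.b:

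1. Patients who used no device and needed no human help at baseline have worsened if at day 60 they use a cane or walker, need human help, cannot walk, or have died.
2. Patients who used a cane or walker without human help at baseline have worsened if at day 60 they need human help, cannot walk, or have died.

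State outright that unchanged device use is not worsening. With rule 1 limited in this way, the conflicting pair is coded once, in line with the lead sentence and rule 2, and no other row of the table changes.

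The cost is one sentence in the SAP and a check that the derivation code matches it, best done before unblinding. There is no statistical downside.

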## VII. Exploratory Analyses

For all exploratory outcomes, summary statistics (frequencies and percentages for categorical variables, means and standard deviations, or medians and IQRs for continuous variables, frequencies and median time to event for time-to-event variables) will be presented by arm. If there are sufficient events for analysis of binary outcomes, the Mantel-Haenszel relative risk, stratified by sex, fracture type, and country, will be estimated.

**VII.1. Inpatient major morbidity and mortality.** Study site personnel collected data on any of the below events occurring prior to death, discharge, or post-randomization day 30 via medical record review using outcome definitions listed in the REGAIN manual of procedures; additional information on postoperative acute kidney injury was obtained by comparison of site-reported pre-randomization creatinine vs peak post-operative creatinine values where available. Except where specified below, all morbidity and mortality endpoints will be analyzed as binary data.

- a. In-hospital death
- b. Myocardial infarction
- c. Troponin elevation without diagnosed myocardial infarction
  - i. Note: Information on peak postoperative troponin values was collected from REGAIN patients based on laboratory data obtained as a component of routine care. Information on isolated troponin elevation (i.e. without a diagnosis of myocardial infarction) will be reported for individuals not otherwise identified as having experienced a myocardial infarction.
- d. Non-fatal cardiac arrest
- e. Stroke
- f. Pneumonia
- g. Pulmonary embolus
- h. Pulmonary edema
- i. Unplanned postoperative intubation or need for mechanical ventilation
- j. Acute kidney injury
- k. Surgical site infection
- l. Urinary tract infection
- m. Any postoperative transfusion
- n. Any return to OR
- o. Need for critical care admission
- p. Fall within 12 hours of anesthesia

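### The cut that defines worsened walking (SAP VII.4.b) depends on baseline device use, but the analysis is not stratified by it and no analysis uses the ordered walking states

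*SAP*

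**What the plan says.** SAP VII.4.b codes a patient as worsened who at day 60 "needed a level of assistance in walking greater than prior to surgery, or if they could not walk at all, or if they died" before then. It then gives two rules:

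- First group: "those who could walk without human assistance at baseline are considered to have worsened" on any of three conditions. In full, the group is "considered to have worsened if at day 60 they required assistance to walk (e.g. cane, walker or human assistance), could not walk at all, or" had died.
- Second group: "Those who required a cane or walkers at baseline are considered worsened if they needed human assistance to walk", cannot walk, or have died.

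The analysis comes from the opening of Section VII: "If there are sufficient events for analysis of binary outcomes, the Mantel-Haenszel relative risk, stratified by sex, fracture type, and country, will be estimated". Baseline use of a cane or walker is not in that list. The SAP does use it elsewhere: VII.2 adjusts time to first ambulation for it, and Section VIII(d) lists need for assistive devices before the fracture as a subgroup variable. No section analyses walking level as an ordered outcome.

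**The concern.** The coding rule needs five day-60 states (unaided, cane or walker, human help, cannot walk, dead) and then keeps one cut. This has two consequences.

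First, the cut lies between unaided and device for baseline unaided walkers, and between device and human help for baseline device users. The event rate is then likely to differ widely between the groups. An analysis that ignores the grouping carries that between-group variation as noise.

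Second, among baseline unaided walkers, starting to use a cane, needing a person's help, not walking and dying are one event. If most of them use an aid at day 60, the event is close to saturated in that group and the relative risk mainly reflects uptake of aids.

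At stake is the precision and readability of one exploratory outcome. Randomization protects the comparison whether or not baseline device use is a stratum.

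**Working it through.** The SAP gives no rate, sample size or effect for this outcome, so there is no figure to reproduce. The only input taken from it is the two-sided 0.05 level (Section IV). State distributions, sample size and odds ratios are assumptions. The first group is read as walking with no aid at all.

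**1. Where the cut falls.**

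| Day-60 state | Baseline unaided | Baseline cane/walker |
|---|---|---|
| Unaided | not worsened | not worsened |
| Cane or walker | worsened | not worsened |
| Human help | worsened | worsened |
| Cannot walk | worsened | worsened |
| Dead | worsened | worsened |

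**2. Information kept by the cut.** Near the null, the efficiency of a binary cut relative to a proportional-odds analysis is RE = 3p(1 − p) / (1 − Σpₖ³), where p is the proportion worsened and pₖ are the state proportions.

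Baseline unaided walkers (states in the order above):

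| Assumed states | p(1 − p) | Σpₖ³ | RE |
|---|---|---|---|
| .50/.30/.10/.05/.05 | .2500 | .1533 | 0.89 |
| .30/.40/.15/.08/.07 | .2100 | .0952 | 0.70 |
| .15/.55/.15/.08/.07 | .1275 | .1740 | 0.46 |
| .08/.70/.10/.07/.05 | .0736 | .3450 | 0.34 |

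The loss runs from 11% to 66%. It is small when half stay unaided and large only when most need a device. For baseline device users, .05/.67/.14/.07/.07 gives RE 0.87 and .10/.45/.22/.13/.10 gives 0.83, a loss of 13 to 17%. If improvement to unaided is not kept as a separate state, the loss is 1 to 9%.

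**3. The two changes separated, in one worked case.** Assume N = 1,400 split 1:1, 65% unaided at baseline, and a common odds ratio of 1.4. Control states are .15/.62/.11/.07/.05 (unaided) and .04/.66/.14/.09/.07 (device users).

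- Worsened, control: .85 and .30. With odds of a better state multiplied by 1.4: .802 and .234.
- Pooled: .65 × .85 + .35 × .30 = .6575 against .65 × .802 + .35 × .234 = .6033, a difference of .0542.
- Planned test, not stratified by device use: variance at the mean proportion .6304 × .3696 = .2330; SE = √(4 × .2330/1,400) = .0258; z = 2.10; power Φ(2.10 − 1.96) = 56%.
- Stratified by device use: within-group variance, at the arm-averaged proportions .826 and .267, is .65 × .826 × .174 + .35 × .267 × .733 = .162; SE = √(4 × .162/1,400) = .0215; z = 2.52; power 71%.
- Ordinal, stratified: V = (N/12)(1 − Σpₖ³) summed over the two groups. With control proportions, (910/12)(1 − .2435) + (490/12)(1 − .2914) = 86.3. Then ln(1.4) × √86.3 = 3.13, power 88%.

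Simulation of the same case gave 57%, 71% and 86%, using a stratified rank test in place of the proportional-odds model. About half of the total gain is from stratification and half from keeping the order.

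**4. Range over assumed state sets** (simulated, N = 1,400, odds ratio 1.4). Power was 49–83% for the planned test, 65–84% when stratified by device use, and 86–90% for the stratified ordinal test. Set by set, stratification added about 1 to 18 points and the ordinal analysis a further 5 to 22.

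**5. When odds are not proportional** (simulated).

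- Only human help, non-walking and death fall: the ordinal test had 28–78% power, while a binary test at the primary endpoint's cut had 72–89%.
- Only the unaided/cane boundary moves: the ordinal test lost up to about 12 points against the stratified binary test.

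**The case against.** The strongest reply is that the contrasts this outcome blurs are tested elsewhere. The primary endpoint counts human help or death as the event, VI.1 tests 60-day mortality, VI.2 tests walking without human help among survivors, and VII.4.a analyses time to death. VII.4.b adds the one boundary those miss, unaided against device. Where treatment acts only on the worse states, the primary cut is the more powerful test. Where it acts only on the unaided/cane boundary, the binary coding is better than the ordinal one. VII.4.b also asks about change from the pre-fracture level as a risk, which a common odds ratio on the day-60 state does not replace. All of this stands. It rules out demoting the binary outcome and limits the ordinal model to a supplement.

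A reader might infer that much of the information held is lost. The SAP gives no state distribution, and the assumed loss runs from slight to about two thirds, so this is not established. A reader might also add the two gains and credit the total to the ordinal analysis, but in the worked case about half comes from stratification. Nor does a new cane count as death for everyone: that holds only for baseline unaided walkers.

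The objection does not answer two things. The cut moves with a baseline variable that is collected and used elsewhere but left out here. And no analysis uses the walking gradient as an order.

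**Conclusion.** The point holds as a modest improvement to an exploratory outcome. The plan's conclusions on death or on walking without human help do not depend on it.

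The firmer part is the missing stratification. It follows from the coding rule itself, needs no proportional-odds assumption, and gained about 1 to 18 points in the assumed scenarios. The ordinal supplement gained a further 5 to 22 points if odds are proportional, and can lose up to about 12 against the stratified binary test if only the unaided/cane boundary moves. These sizes rest on assumed state distributions, 1,400 patients and an odds ratio of 1.4.

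It would be tempting to call the planned analysis biased or invalid. The documents do not support that: assignment is randomized, and simulated null rejection rates were 4–5% for all three tests. What is lost is precision and detail.

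A sharper defect in the same item must be settled first. As written, the first group includes baseline cane users who walk without a person's help. An unchanged cane user is then worsened under the first rule and not worsened under the second.

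**What to change.** 1. In VII.4.b, reconcile the two baseline-group definitions so that each patient falls under exactly one rule.
2. Keep the binary worsened outcome and its Mantel-Haenszel relative risk, but add baseline cane or walker use to sex, fracture type and country as a stratum.
3. Add, as supplementary, a proportional-odds model of the five day-60 states (unaided, cane or walker, human help, cannot walk, dead), adjusted for the same four factors. Report the common odds ratio with its 95% confidence interval and the odds ratio at each cut.
4. Tabulate the five states by arm and baseline device use. The table is also needed to read the pooled relative risk: in the worked case one odds ratio of 1.4 gives .802/.85 = 0.94 in unaided walkers and .234/.30 = 0.78 in device users.

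Cost: SAP wording and one extra model on data that the coding rule already requires. The strata double from 8 to 16. An odds ratio is less direct than a relative risk, and the model assumes roughly proportional odds, which the cut-specific odds ratios let the reader check. The primary endpoint is unchanged.
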